6.5 Safety Assessments

6.5.1 *Extent of Exposure and Compliance to Study Treatment*

6.5.1.1 *Extent of Exposure to TheraSphere*

TheraSphere exposure will be presented as described below for the Treatment arm. This includes summaries presented separately for TheraSphere administered prior to progression (i.e. prior to date of progression) and post progression (i.e. on or after date of progression) as assessed by investigator according to RECIST 1.1.

- Number of patients who received TheraSphere during the study
- Number of patients who received TheraSphere prior to progression and post progression
- Reasons for not receiving TheraSphere prior to progression
- Reasons for not receiving a second TheraSphere administration prior to progression for patients with bilobar disease
 - Note that bilobar disease is from the stratification factor on the Randomization eCRF page, with any incorrect values at randomization replaced with the corrected value from the eCRF, or values from eCRF for patients enrolled after the changes in stratification factor; this rule also applies to the derivation of unilobar or bilobar disease in later bullets
- Number of patients with bilobar disease at baseline who received TheraSphere prior to progression
 - to both lobes or to the whole liver (i.e. TheraSphere administered to both lobes in a non-lobar approach, for example through the common hepatic artery) on the same day,
 - to both lobes on different days,
 - to both lobes ≥ 28 days apart
 - to both lobes < 28 days apart
 - to one lobe
- Number of patients with unilobar disease at baseline who received TheraSphere prior to progression
 - to both lobes or to the whole liver on the same day,
 - to both lobes on different days,
 - to both lobes ≥ 28 days apart
 - to both lobes < 28 days apart
 - to one lobe
- Number of patients who received first TheraSphere administration post progression

- Patients with at least one TheraSphere administration not completed as planned prior to progression and separately post progression
- Time to the first angiogram (days) prior to progression, defined as (first angiography date prior to progression – randomization date + 1)
- Time to the first TheraSphere treatment (days) prior to progression, defined as (treatment date of first TheraSphere administration prior to progression - randomization date + 1)
- TheraSphere dose absorbed by perfused volume prior to progression and post progression
- TheraSphere dose delivered to lungs prior to progression and post progression

TheraSphere dose absorbed by perfused volume will be calculated as follows.

- Dose absorbed by perfused volume within a lobe (left lobe or right lobe) is defined using data for the corresponding lobe, as the sum of doses delivered by each vial if multiple vials are used to treat same target tissue, or as the weighted average of doses delivered by each vial (weights are target tissue masses) if multiple vials are not used to treat same target tissue.
- Dose absorbed by perfused volume within the liver is defined as the weighted average of doses delivered to each lobe (weights are the sum of target tissue masses in each lobe) for patients who had both lobes treated, and as the single dose delivered for patients who received whole liver dosing.
- Dose absorbed by perfused volume is defined as the dose absorbed by the perfused volume within the treated lobe for patients who had one lobe treated, and dose absorbed by the perfused volume within the liver for patients who had both lobes treated or who received whole liver dosing.

TheraSphere dose delivered to lungs will be calculated as the sum of doses delivered to lungs across all TheraSphere administrations.

6.5.1.2 Extent of Exposure to Sorafenib

Sorafenib exposure prior to progression (i.e. prior to date of progression) as assessed by investigator according to RECIST 1.1, will be presented as described below by treatment group.

- Number of patients who received sorafenib during the study
- Number of patients who received sorafenib prior to progression
- Reasons for not receiving sorafenib prior to progression
- Time to the start of sorafenib (days) prior to progression, defined as (start date of first sorafenib administration prior to progression - randomization date + 1)
 - This summary will also be produced separately for patients with unilobar and bilobar disease at baseline (Note that unilobar or bilobar disease is

from the stratification factor on the Randomization eCRF page, with any incorrect values at randomization replaced with the corrected value from the eCRF, or values from eCRF for patients enrolled after the changes in stratification factor)

- Cumulative dose (g) of sorafenib prior to progression
- Dose intensity (mg/day) of sorafenib prior to progression
- Relative dose intensity (%) of sorafenib prior to progression
- Duration of treatment (weeks) of sorafenib prior to progression
- Reason for Dose Delays and Changes for sorafenib prior to progression

6.5.1.3 Extent of Study Exposure

The duration on study will be determined.

6.5.1.4 Best Available Care Post-Progression

Systemic treatments and liver directed therapies received post-progression according to RECIST v1.1 by investigator assessment will be summarized as follows:

- Systemic treatments received post-progression
 - from the “Best Available Care - Post Treatment Discontinuation – Medication” eCRF page with start date on or after date of progression, by preferred terms (classification based on World Health Organization Drug Enhanced [WHO DE] March 2011)
 - from the “Sorafenib Administration” eCRF page with start date on or after date of progression
- Liver directed therapies received post-progression
 - from “Additional Procedures” eCRF page with start date on or after date of progression, categorized according to a manual review of the free text entered in the “Procedure term” eCRF field
 - from “TheraSphere Doses Administered” eCRF page with treatment date on or after date of progression

6.5.2 Adverse Events

All adverse events (AEs) will be documented from the date of randomization until study exit. For patients who permanently discontinue sorafenib in either arm of the study, AEs will be documented for 30 days from the date of discontinuation. After this period, only AEs considered to be related to TheraSphere will be collected.

A treatment emergent AE (TEAE) is defined as an event that was not present at baseline or worsened in severity following the start of treatment through to 30 days after the end of the last study treatment (sorafenib and/or TheraSphere) initiated prior to progression

date by investigator assessment, or start date of subsequent HCC therapy, whichever comes first.

The start of treatment will be defined as the start date of sorafenib and the date of first angiogram, prior to progression date by investigator assessment, whichever occurs first. The last study treatment will be sorafenib for patients who received only sorafenib or both sorafenib and TheraSphere prior to progression, and will be TheraSphere for patients who only received TheraSphere prior to progression. Partial AE start and stop dates will be imputed as described in Section 6.2.1.3.

The investigator's verbatim term of an AE will be mapped to a system organ class and preferred term using the MedDRA Version 14.0 dictionary (Medical Dictionary for Regulatory Activities). The investigator will use the NCI Common Toxicity Criteria for Adverse Events [CTCAE] (version 4.0) or the protocol specific criteria when no NCI CTC criteria are available for the AE to determine the severity of the AE.

Adverse events related to sorafenib, device, and angiographic procedures are defined as those events recorded on the eCRF with relationship of possibly, probably, or definitely relationship. Relation to TheraSphere (device) is not appropriate for the Control group.

The incidence of TEAEs will be the number of patients who had the AE (counted only once) divided by the number of patients in the safety population and represented as a percentage. For subgroup summaries of AEs, the percentage will be represented as the number of patients with the AE event divided by the number of patients of that group in the safety population. The incidence of AEs will be the number of times an event occurs, counting worsening events only once. For worsening events, the AE end date of the earlier AE will be the same as the start date of the same AE with a higher severity.

Adverse events reported for the Treatment group patients will be split further into three groups, all TEAEs, TEAEs after angiogram before start of sorafenib, and TEAEs after start of sorafenib.

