12.2 RECORDING ADVERSE EVENTS

All adverse events and adverse device effects will be documented from the date of randomization until study exit. For patients who permanently discontinue sorafenib in either arm of the study, AEs will be documented for 30 days from the date of discontinuation. After this period, only AEs considered to be related to TheraSphere will be collected.

In this study, patients should be encouraged to report adverse events spontaneously or in response to general, non-directed questions. At any time during the study, the patient may volunteer information that resembles an adverse event. Once it is determined that an adverse event has occurred, the Investigator should obtain all the information required to complete the adverse event form. Any medical management of an event and the date of resolution of the event must be recorded in the source document and on the appropriate case reports form(s) using medical terminology according to sponsor instructions.

For each AE, the following information will be recorded:

- Adverse event
- Serious/non-Serious
- Severity (Toxicity Grade)
- Action taken
- Relationship to study treatment
- Expected/Unexpected
- Date and time of onset
- Date and time of resolution

An expected adverse event is any AE, the nature or severity of which is identified in the relevant Package Insert.

Any AE experienced by a subject will be followed until the AE has resolved to the investigator's or physician sub-investigator's satisfaction. If a problem still exists, then the investigator or physician sub-investigator at his/her discretion will ask the subject to come back to the clinic for further evaluation. Any serious adverse events should be managed as discussed in Section 12.3.

Once the subject has been discharged from the study, the investigator has no obligation to seek further follow-up with the subject in order to identify new AEs. However, if the investigator becomes aware of an SAE that has occurred following the subject's discharge from the study and the investigator considers the SAE possibly, probably, or definitely related to a study drug or device, then the investigator should report the SAE as described in the protocol.

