17.0 STUDY TERMINATION

The sponsor reserves the right to discontinue this study for administrative reasons at any time. The end of the study is defined as the reaching of the required number of deaths and all TheraSphere treated patients have been followed-up for a minimum of 30 days from the last TheraSphere treatment, and all sorafenib treated patients in the control arm have been followed-up for a minimum of 30 days after the last dose of sorafenib.

APPENDICES

1. TheraSphere Product Labeling
 - a. US Package Insert
 - b. CA Package Insert
 - c. EU Instructions for Use
4. Child Pugh Classification

Assess severity of liver disease by assigning points for each of the five parameters in the table below and adding the points to obtain a total score. Record the resulting Child Pugh Grade: A (well compensated disease) 5-6 points; B (functional compromise, worsening disease) 7-9 points and C (decompensated disease) 10-15 points.

Parameter	1 point	2 points	3 points
Bilirubin	<34 µmol/L	34–50 µmol/L	>50 µmol/L
Albumin	>35 g/L	28-35 g/L	<28 g/L
Prothrombin Time	<1.8 (INR) or <4 secs (Seconds over control)	1.8-2.2 (INR) or 4-6 secs	>2.2 (INR) or >6 secs
Ascites	absent	Slight (medically controlled)	Moderate (poorly controlled)
Encephalopathy*	None	Grade 1-2	Grade 3-4

*Grades of Encephalopathy

Grade 1 – Inverted sleep pattern; forgetfulness, agitation, irritability, apraxia

Grade 2 – Lethargy; Disorientation for time or place, Subtle personality change; Asterixis, ataxia

Grade 3 – Somnolence but rousability; Disorientation as regards place; Asterixis, hyperactive reflexes, Babinski signs, muscle rigidity

Grade 4 – Coma (unresponsive to verbal or noxious stimuli)

REFERENCES

¹<http://www.dep.iarc.fr/> accessed July , 2015

² <http://www.fda.gov/AboutFDA/CentersOffices/CDER/ucm129234.htm>, accessed June 22, 2010 at 09:30 ET

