5.2.5 Analysis Population

For the Per Protocol population, the protocol states that patients in this population will be analyzed according to the treatment actually received. Since patients who did not receive the treatment they were randomized to receive prior to progression by investigator assessment will be excluded from the Per Protocol population, the treatment actually received will be identical to the treatment randomized to receive. Hence, patients in this population will be analyzed according to the treatment group to which they were randomized.

For the safety analysis population, the protocol defines this population as all randomized patients who received at least one administration of study treatments and will be analyzed according to the treatment actually received. However, for patients with progression by investigator assessment, only study treatments received prior to progression will be used in the derivation of this population. Since both TheraSphere and sorafenib are allowed as best available care post progression, there are patients who received part of their randomized study treatment only after progression.

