8.7.2 Adverse Events

The investigator's verbatim term of each AE will be mapped to system organ class and preferred term using the MedDRA Version 14.0 dictionary.

Adverse events will be summarized by system organ class and preferred term; a patient will only be counted once per system organ class and once per preferred term within a treatment. Patient counts and percentages and event counts will be presented for each treatment group for the following summaries:

1. Overall summary of TEAEs
2. All TEAEs (also presented by preferred term only in descending order).
3. All TEAEs with CTCAE grade ≥ 3 (also presented by preferred term only in descending order).
4. All TEAEs considered related to sorafenib.
5. All TEAEs considered related to device (ADE).
6. All CTCAE grade ≥ 3 TEAEs considered related to device.
7. All TEAEs related to angiographic procedure.
8. All TEAEs with fatal outcome.
9. All treatment emergent serious adverse events (SAE).
10. All treatment emergent serious adverse device events (SADE)
11. All TEAEs leading to sorafenib discontinuation
12. All TEAEs of special interest (presented by AESI category and preferred term)
13. All TEAEs of special interest with CTCAE grade ≥ 3 (presented by AESI category and preferred term)

Event rate (per 100 patient years) will also be presented by treatment group for each of the above TEAE categories. For each category, the event rate is defined as the number of patients with TEAEs in that category divided by the total duration of patients at risk for TEAEs and then multiplied by 365.25×100 to present in terms of per 100 patient years.

For the summary of TEAEs by CTCAE grade, if a patient has multiple events occurring in the same body system or same preferred term, then the event with the highest CTCAE grade will be counted. For TEAEs by relationship to study device, if a patient has multiple events occurring in the same body system or same preferred term, the event with the highest association to study device will be summarized (unknown is considered a higher association to study device than not related, but less of a relationship than possibly, probably, and definitely). Adverse events related to sorafenib, device and angiographic procedure are defined as a subset of AEs with a relationship of either possibly, probably, definitely, or unknown.

No statistical inference between the treatments will be performed on AEs.

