Listings will be presented by patient for all AEs as well as for SAEs including SADE, AEs with fatal outcome, and AEs leading to discontinuation of sorafenib.

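### The device-effect tables in SAP 8.7.2 use a TEAE window that post-progression TheraSphere cannot extend, so later device effects are listed but not tabulated

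*SAP*

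**What the plan says.** - **Window.** SAP 6.5.2 counts an event as treatment-emergent "through to 30 days after the end of the last study treatment (sorafenib and/or TheraSphere) initiated prior to progression" (investigator-assessed), or up to subsequent HCC therapy if that starts sooner. Sorafenib sets the end for anyone who took it before progression. TheraSphere sets it only for patients who had TheraSphere alone before progression.
- **Tables.** SAP 8.7.2 lists 13 summaries, all restricted to treatment-emergent events; item 5 begins "All TEAEs considered related to device (ADE". The further split of Treatment-group events in 6.5.2 ("all TEAEs, TEAEs after angiogram before start of sorafenib, and TEAEs after start of sorafenib") stays inside the same window.
- **Listings.** Also in 8.7.2: "Listings will be presented by patient for all AEs as well as for SAEs including SADE, AEs with fatal outcome". These carry no treatment-emergent restriction.
- **Collection.** Protocol 12.2 collects all AEs for 30 days after permanent sorafenib discontinuation. Then: "After this period, only AEs considered to be related to TheraSphere will be collected".
- **Status of later TheraSphere.** Protocol 3.0, footnote 4, reserves additional TheraSphere for progression, and the synopsis allows up to two re-treatments. SAP Appendix 4 classes these in the TheraSphere arm as study treatment, not as subsequent HCC therapy. SAP 6.5.1.1 tabulates post-progression TheraSphere exposure.
- **Disclosure.** SAP 5.2.6 declares the cut-off as a change from the protocol and gives two reasons: comparability of the groups, and keeping the effect of subsequent HCC therapy out of the AE profile.

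**The concern.** The trial's stated objective is to evaluate TheraSphere. The SAP plans tables of the dose given after progression, but no matching table of the harms that investigators attribute to it. SAP 5.2.5 confirms that such use occurred: "Since both TheraSphere and sorafenib are allowed as best available care post progression, there are patients who received part of their randomized study treatment" only once they had progressed. A device effect that falls after the window is collected and attributed, but it adds nothing to any ADE, SADE, grade 3 or higher device-related, or fatal-event table. A reader who takes those tables as the device's safety record would see too few affected patients, and would have to rebuild the count from listings that give no percentage and no denominator.

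The denominator has a related limit. SAP 8.3.2 groups patients by treatment received before progression. A Treatment-group patient whose first TheraSphere came after progression is therefore not counted as TheraSphere-treated, and one with no study treatment before progression is outside the Safety Population altogether.

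**Working it through.** **1. How many summaries are restricted.** In SAP 8.7.2, items 1 to 8 and 11 to 13 refer to TEAEs (11 items). Items 9 (SAE) and 10 (SADE) are worded as treatment emergent (2 items). 11 + 2 = 13 of 13.

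**2. Whether a re-treatment can move the window.** The window depends only on treatment begun before progression. Additional TheraSphere comes only after progression. It therefore never sets or extends the end date. Because Appendix 4 does not count it as subsequent HCC therapy, it does not close the window either.

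**3. How many days after a re-treatment are covered.** Inputs:
- 30-day tail (SAP 6.5.2)
- sorafenib stopped at least 7 days before re-treatment (Protocol 9.2.15.1.6; 3.0 footnote 6)
- sorafenib restarted 2 weeks after (same footnote)
- at least 28 days since the last TheraSphere to that lobe (Protocol synopsis)

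Days covered = 30 − (days from the end of the window-setting treatment to the re-treatment), with a floor of 0. Any cut for subsequent HCC therapy comes on top.

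| Situation | Days covered after re-treatment |
|---|---|
| Sorafenib stopped ≥ 7 days before, restart not counted | 30 − 7 = at most 23 |
| Sorafenib ended more than 30 days before | 0 |
| TheraSphere only, re-treated in the lobe last treated | 30 − 28 = at most 2 |
| Same patient, second re-treatment of that lobe (≥ 28 + 28 = 56 days) | 0 |
| Sorafenib resumed and counted as the pre-progression course | at least 14 + 30 = 44 |

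The last row is the less likely reading. SAP 6.5.1.4 and 8.7.1.2 sort sorafenib records by whether their start date precedes progression, which suggests that a restart after progression does not count. SAP 6.5.2 does not say so itself.

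**4. Whether the stated reasons reach the device tables.** The comparability reason does not: SAP 6.5.2 states "Relation to TheraSphere (device) is not appropriate for the Control group", so there is no between-arm device comparison for a progression cut-off to protect. The second reason does: once another liver-directed or systemic therapy has started, attribution to the device is less secure. What lacks a device-specific reason is the cut at progression, not the cut at subsequent HCC therapy.

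**5. Other aggregate outputs.** SAP 8.7.3 and 8.8 plan shift tables for laboratory grades, ALBI, ECOG and Child-Pugh. These are not cut at progression, but they carry no device attribution. SAP 7.7 plans subgroup summaries of AEs without the treatment-emergent qualifier; they are not device-specific, and 8.7.2 appears to govern them. Section 6.6 and part of 8.9 are redacted and could not be checked.

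**The case against.** The strongest reply is that this is an openly declared choice with a rationale, that AE summaries carry no inference, and that nothing is lost. All AEs, SAEs including SADEs, and fatal AEs are listed. SADEs and UADEs reach the sponsor within 24 hours (Protocol 12.3), and the IDMC reviews safety. All of that stands, and it limits the point to how device safety is described. It does not supply a count, a percentage or a denominator for device effects after protocol re-treatment.

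Four stronger readings are tempting and are not supported:

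- *The window breaks a protocol commitment.* Protocol 17.0 ends the study only when "all TheraSphere treated patients have been followed-up for a minimum of 30 days from the last TheraSphere treatment". That defines when the study ends. It sets no AE analysis window, so days covered should not be scored as a shortfall against it.
- *Neither reason in SAP 5.2.6 applies to device tables.* The reason about subsequent HCC therapy does apply, as step 4 of the check shows.
- *No aggregate safety information exists after progression.* The shift tables in 8.7.3 and 8.8 provide some, without attribution.
- *The SAP confines every safety display to the Safety Population.* Sections 8.3.2 and 8.7 say so in general terms, but 8.7.1 runs exposure on the mITT and PP populations as well, and 8.8 runs the ECOG and Child-Pugh shifts on mITT. A local statement of population is therefore established practice in this SAP.

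**Conclusion.** The point holds as a gap in tabulation. It is not a contradiction, an undisclosed change or a loss of data. Applied as written, SAP 8.7.2 can understate the crude number and percentage of patients with device effects, because events attributed to TheraSphere after the window appear in that section only as listings.

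The size is unknown: the documents give neither the number of patients re-treated after progression nor the number of late device events. The day counts (at most 23, at most 2, or 0) show how little of the period after a re-treatment may be covered. They rest on the protocol's minimum intervals and, for the 23-day figure, on the restart of sorafenib not counting. They do not estimate missed events. Rates per 100 patient-years could move either way, since the window also limits the time at risk. Overall survival and the other efficacy analyses are unaffected. The change is worth making because it is cheap and concerns the product under evaluation.

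**What to change.** Keep all 13 TEAE tables for the between-arm description. Then:

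1. Add to SAP 8.7.2 one supplementary descriptive ADE/SADE display (all grades, grade 3 or higher, serious, fatal) for all Treatment-group patients who received any protocol TheraSphere. Run it from first angiogram to study exit, split before and after progression, and flag events after the start of subsequent HCC therapy.
2. State the population for that display in 8.7.2 itself, as 8.7.1 and 8.8 do for theirs. No amendment of 8.3.2 or 8.7 is needed.
3. In 6.5.2, cross-reference the start-date rule of 6.5.1.4 and 8.7.1.2, so that it is clear whether sorafenib resumed after progression extends the window.

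The cost is one display from data already collected, somewhat larger than a standard table because of the split and the flags, plus two short additions to the text. No alpha is spent. The downsides are a longer safety section, higher reported device-event counts, and less certain attribution for the flagged events.
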